#### 3.5 Secondary endpoints/outcomes

Quality of life: Sepsis, such as can be caused by cIAI relapse, impacts quality of life over a prolonged period of time. The impacts of sepsis map closely onto the components of a quality-of-life measure e.g., the EQ-5D-5L. We will therefore measure the EQ-5D-5L multiple times over the 180 days following cIAI randomisation.

Desirability Of Outcome Ranking (DOOR) [25]: Patients will be categorised according to the worst outcome they experience over the six month follow up period using a four-level ordinal classification. The four levels will be 1. No treatment failure, 2. Treatment failure (as for the primary outcome), 3. Treatment failure associated with sepsis (NEWS 6 in ward-based patients and SOFA 2 in ICU based patients [22]). Treatment failure associated with death. Note, sepsis and death must occur within 5 days of antibiotic treatment starting or changing.

Other secondary outcome measures: time to treatment failure, number of episodes of treatment failure, number and type of source control procedures, relapse of cIAI, all-cause mortality (time to event), length of hospital stay, re-admission, C. difficile infection, anti-microbial resistant (AMR) infections within 180 days of antibiotic therapy, days of antibiotic therapy (in-patient and outpatient,

including anti-fungal therapy), acute kidney injury, complications, days of ventilation and days of renal replacement therapy.

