Number and type of source control procedures: In-patient operation notes and radiological reports will be monitored to determine the total number of source control procedures and their type (radiologically guided (Ultrasound scan, CT) or surgical (open, laparoscopic)). The definition of source control used for this study is any procedure that stops the ongoing contamination of the peritoneal cavity and removes the majority of the contaminated intraperitoneal contents to the extent that no further acute interventions are felt to be necessary. Depending on the site and origin of the infection, multiple techniques could be satisfactory to obtain source control. Acceptable procedures might include simple drainage via open, laparoscopic, or percutaneous means, repair of a perforated viscus, resection and primary re-anastomosis of a perforated viscus, resection of a perforated viscus and proximal diversion, or proximal diversion without resection as long as adequate drainage is obtained. Note, where the abdomen is left open following a surgical procedure a procedure to close the abdomen will be counted as a second and separate procedure,

Relapse of cIAI: In patients with an episode of treatment failure up to 180 days after randomisation, senior clinicians from the patient's primary care team will be asked to report if the patient had a relapse or not, and the date of the first relapse.

Antimicrobial resistant (AMR) infection: When standard treatment fails in patients with cIAI, antibiotics are often escalated to one of the carbapenem class of antibiotics. We will therefore use rates of carbapenem prescribing as a surrogate for AMR infections. Whilst all surrogates of AMR infection have limitations, this measure is important to both patients and clinicians and should be an effective AMR surrogate measure across a large number of sites.

Further, we will complete passive surveillance of AMR infection across the six month follow up period. Susceptibility patterns of bacterial isolates identified as part of routine clinical practice will be collated from microbiology laboratories to identify AMR including MRSA, VRE, ESBL and CPE. Detection of any AMR infection (MRSA, VRE, ESBL and CPE) will be a secondary outcome. Also, antimicrobial treatments will be analysed for the number of antibiotic class switches. We do not consider it feasible to standardise the investigation of infections for patients with acute infections to allow active surveillance of AMR.

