## 8.2 Detailed specification of the intervention

The intervention is a strategy of a fixed-extended-duration antibiotic treatment of 28-days. The start of antibiotic therapy is the first day of effective therapy for cIAI treatment, which will generally occur before randomisation, but could be following randomisation if antibiotics given prior to randomisation are ineffective/inactive. The start date of antibiotic treatment will be determined by the patient's clinical team or clinical research team. Examples of antibiotic therapy that are not therapy for cIAI include antibiotic prophylaxis, or treatment for other infections e.g., cystitis. All treatment will be considered effective unless:

1) Antimicrobial resistance is identified on clinical samples collected before randomisation and that resistance is believed to be clinically relevant i.e., antibiotic treatment is changed based on the microbiological evidence of antibiotic resistance. The start date of fixed-extended-duration antibiotic treatment of 28-days will be re-set to day 0 where antibiotic treatment is changed based on pre-randomisation detection of antibiotic resistance. This strategy relates to the fixed-extended-duration treatment only, and the date of randomisation is not changed.

2) Antibiotics are prescribed for prophylaxis e.g., penicillin for splenectomy, elective surgery antibiotic prophylaxis, UTI prophylaxis

3) Antibiotics are prescribed for the treatment for other infections e.g., cystitis, and not effective against cIAI.

4) Antibiotics are oral antibiotics prescribed prior to hospitalisation

5) Antibiotics from a previous course of antibiotics, a previous course is one stopped for 48 hours or more.

The choice of antibiotic and route of administration are therefore selected by the treating clinician. Source control procedures (surgical and radiological) will be carried out as per standard practice.

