#### Anti-microbial resistant infections

Participants will undergo passive surveillance for antimicrobial resistant infections (including MRSA, VRE, ESBL and CPE) during the 180 days following randomisation. The proportion of patients that experience each type of antimicrobial infection, number of days receiving carbapenem class antibiotics and the number of antibiotic class switches will be reported descriptively by randomised group and overall. Incidence of any antimicrobial resistant infection will be analysed using a mixed effect logistic regression model with fixed effects for allocation, the stratification factors and other prognostic baseline covariates, and random intercepts for study recruitment site. The estimated conditional odds ratio for allocation, 95% confidence interval and p-value will be reported. Point estimates and appropriate two-sided 95% confidence intervals for the relative risk (cases/non-cases) and absolute risk reduction (based on the fitted model) will be reported, with fixed effect covariates held at representative values. Average marginal effects on both the risk ratio and risk difference scales will also be reported with appropriate two-sided 95% confidence intervals. The number of days receiving carbapenem class antibiotics and the number of antibiotic class switches will be modelled using a proportional odds model, with fixed effects for allocation, the stratification factors and other prognostic baseline covariates, and random intercepts for study recruitment site. This model will be used to derive the difference in mean number of class switches and days receiving carbapenem. conditional on pre-specified representative values of the fixed effect covariates, as well marginal effects (on both the risk ratio and risk difference scales) conditional on pre-specified representative values of the fixed effect covariates (e.g. Pr(Y > 0 | Intervention, X)/Pr(Y > 0 | Control, X) for covariates X). Average marginal effects (on both the risk ratio and risk difference scales) will also be reported together with appropriate 95% confidence intervals for various relevant outcomes/cut-offs. Data on antimicrobial resistance will be used, in conjunction with antibiotic prescribing data, to assess the appropriateness of antibiotic therapy. Appropriateness will be assessed by a blinded clinician, and will be assigned as inappropriate, appropriate, or not determined.

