## The EXTEND Trial protocol

## ISRCTN no. 72819021

Surgical or radiological interventions	Pancreatitis Perforated peptic ulcer Perforated small bowel Perforated large bowel Pelvic inflammatory disease Post-operative complication (< 90 days) Ulcerative colitis Spontaneous Volvulus Unknown Other (please state) Radiological (CT guided) percutaneous drainage (+/- drain insertion) Radiological (U/S guided) percutaneous drainage (+/- drain insertion) Surgical: Resection and anastomosis (+/- drain insertion) (+/-washout) Surgical: Drainage only (+/- drain insertion) (+/-washout) Surgical: Resection and proximal diversion (+/-washout) Surgical: Closure of perforation only (+/- drain insertion) (+/- washout) Surgical: Drainage and diversion	RN/Clinician	Categorical
	(+/- drain insertion) (+/-washout) Surgical: Excision of damaged		
	insertion) (+/-washout) Surgical: Washout only (+/- drain		
	None of the above: Hepatobiliary surgery		
	None of the above: Pancreatic surgery None of the above: Colorectal		
	surgery None of the above: Radiological procedure		
	None of the above: Other The patient has had no surgical or radiological procedures to remove the infection		
Radiological findings when available	Collection (Y/N) Single collection (Y/N) Multiple collections (Y/N) Maximum depth of collection (cm) Evidence of anastomotic leak (Y/N) Evidence of fistulation (Y/N)	RN/Clinician	Categorical Categorical Categorical Continuous Categorical Categorical
Antibiotic treatment	Antibiotic/Start date/End	RN	Categorical Categorical
Other infection	date/Dose/Frequency Clinical assessment	RN	Categorical
AMR infection	Microbiological results MRSA/ESBL/AMPC/CPE/VRE	RN	Categorical
ICU stay in the 30 days before randomisation	Number of days	RN	Categorical
Ventilation in the 10 days before randomisation	Number of days	RN	Categorical

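### The AMR-infection outcome models any detection as incidence, without separating new resistance from re-detected baseline organisms, and its 180-day window is stated inconsistently

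*Protocol*

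**What the plan says.** **Outcome.** Protocol section 3.6 states that "Detection of any AMR infection (MRSA, VRE, ESBL and CPE) will be a secondary outcome". The source is passive: "Susceptibility patterns of bacterial isolates identified as part of routine clinical practice will be collated from microbiology laboratories to identify AMR".

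**Analysis.** Under Anti-microbial resistant infections in section 10.2.4, "Incidence of any antimicrobial resistant infection will be analysed using a mixed effect logistic regression model". The model has fixed effects for allocation, the stratification factors and further prognostic covariates that are not named. Section 10.2.1 puts all randomised participants with outcome data into each model unless stated otherwise, and nothing is stated otherwise here.

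**Window.** Section 3.5 lists "anti-microbial resistant (AMR) infections within 180 days of antibiotic therapy". Section 3.6 says "we will complete passive surveillance of AMR infection across the six month follow up period". The analysis section has surveillance for resistant infections "including MRSA, VRE, ESBL and CPE) during the 180 days following randomisation". The Trial Summary heads these secondary outcomes as measured from day 0 to day 180.

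**Baseline.** Appendix 3 has an AMR infection row with the options "MRSA/ESBL/AMPC/CPE/VRE". Section 8.2 foresees resistance found on samples taken before randomisation, because it re-sets the start of the 28-day course when treatment is changed for that reason. It also says that effective therapy has a start date "which will generally occur before randomisation, but could be following randomisation if antibiotics given prior to randomisation are ineffective/inactive".

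**The concern.** Incidence normally means new occurrence in people free of the condition at the start. The protocol names incidence but defines detection. A participant whose index infection grew an ESBL producer becomes a case if a drain, wound or blood sample grows the same organism after randomisation. So does a participant who first acquires resistance during follow-up. Only the second is resistance arising after allocation, yet the two are counted alike. The baseline data that would separate them are collected, but no stated outcome rule uses them.

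The window adds to this. If the 180 days of section 3.5 run from the start of therapy, they can cover isolates taken before randomisation. If they run from the end of therapy, the period differs in length by arm, because allocation sets the length of therapy.

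At stake is how a null result would be read. The Rationale gives resistance as the reason why shorter courses are generally favoured, and argues that this fails when short courses have to be repeated. A diluted comparison could be taken as evidence that 28 days carries no resistance penalty.

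**Working it through.** **1. Windows side by side.** The analysis section, section 3.6 and the Trial Summary agree on follow-up time from randomisation. Section 3.5 does not.
- *From the start of therapy:* sections 6.1 and 7.2.1 allow randomisation up to 10 days into treatment, so up to 10 days before randomisation could fall inside the window.
- *From the end of therapy:* with 28 days in one arm and the audit median of 12 days (section 1) taken as typical of the other, therapy ends about 28 - 12 = 16 days later in the extended arm. The time covered, measured from randomisation, shifts by that much between arms.

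**2. The plan's own figure.** Section 10.1 gives no rate, effect or power for AMR, only the primary-outcome sample size. For 50% v 40%, two-sided 5% and 90% power, the pooled two-proportion formula gives 519 per arm; the plan has 524, which yields power 0.903. Then 524/0.9 = 582.2, rounded up to 583 per arm, or 1166. This reproduces and is not affected by the present point. I use 524 per arm below.

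**3. Dilution model (all rates are assumptions).** Let p be the risk of new AMR infection, b the share positive at baseline, and c the share of those re-detected after randomisation. The observed risk is

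q = b[c + (1 - c)p] + (1 - b)p = p + bc(1 - p).

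With the same b and c in both arms, the risk difference is multiplied by (1 - bc). Power = Φ[(d - 1.96·se0)/se1], where d is the risk difference, se0 uses the pooled variance and se1 the unpooled.

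Take p = 10% (standard) v 15% (extended) and b = 10%:

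| c | Observed risks | Risk difference (points) | OR | Power |
|---|---|---|---|---|
| 0 | 10.0% v 15.0% | 5.0 | 1.59 | 0.69 |
| 25% | 12.25% v 17.125% | 4.875 | 1.48 | 0.61 |
| 50% | 14.5% v 19.25% | 4.75 | 1.41 | 0.54 |
| 100% | 19.0% v 23.5% | 4.5 | 1.31 | 0.43 |

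Worked row, c = 25%: d = 0.04875, se0 = √(0.146875 × 0.853125 × 2/524) = 0.02187, se1 = √[(0.1225 × 0.8775 + 0.17125 × 0.82875)/524] = 0.02182. Then (0.04875 - 1.96 × 0.02187)/0.02182 = 0.27, and Φ = 0.61. The last row is a bound, not an expectation.

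**4. Unequal re-detection.** Re-detection happens after randomisation and may differ by arm. With b = 10% and the same p:
- 40% re-detected in the extended arm v 50% in standard care gives 18.4% v 14.5%, OR 1.33, power 0.40.
- 50% v 40% gives 19.25% v 13.6%, OR 1.51, power 0.69.
- 50% v 25% gives 19.25% v 12.25%, OR 1.71, which is above 1.59.

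Dilution is therefore the likely result but not a certain one.

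**5. Counting new types only, everyone kept.** If baseline-positive participants acquire a further type at the same rate as others, the comparison is 10% v 15% (OR 1.59, power 0.69). If they never register a new event it is 0.9 × 10% = 9.0% v 0.9 × 15% = 13.5% (OR 1.58, power 0.64).

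**The case against.** **The detail may be in the SAP.** Section 10.2.4 gives brief details and leaves full specification to the SAP, and the unnamed covariates could include baseline AMR. This stands in part: adjustment would remove much of the dilution of the conditional odds ratio. It would not change the outcome that section 3.6 fixes or the proportions reported, nor would it restore the absolute difference. The window conflict lies within the protocol itself.

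**Any resistant infection is a legitimate question.** It counts what participants actually experience after randomisation and fits the intention-to-treat principle. Persistence of a baseline organism may also be something that duration changes. This is fair, and it is why any detection should be kept alongside rather than dropped. It does not justify labelling the mixture as incidence.

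**Stronger readings a reader might infer, which the documents do not support:**
- *That the section 3.5 window includes the index culture.* The text gives no anchor and never mentions that culture. One taken before the first dose would fall outside even a window from the start of therapy.
- *That carried-over events are fixed before allocation and equal between arms.* Under the analysis section's window they arise only through detection after randomisation, which allocation may influence.
- *That AMR is the trial's main harm comparison.* The Rationale raises resistance but ranks no harm. AMR infection is one of several secondary outcomes, beside C. difficile and acute kidney injury, and resistance is also approached through carbapenem days and antibiotic class switches.
- *That the loss of power is large and known.* No AMR rates are given, and the steepest figures require every baseline-positive participant to be re-detected.

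**Conclusion.** The point holds in a limited form. Any detection, modelled as incidence, mixes new resistance with re-isolation of baseline organisms, and the section 3.5 window cannot be reconciled with the analysis section as written. Re-detection is likely to pull the comparison towards no difference. The moderate fall in odds ratio and power shown for 25-50% re-detection rests wholly on assumed rates of new AMR, baseline positivity and re-detection, and on re-detection being equal in the two arms. Its true size cannot be established from the documents. The primary outcome and the sample size are unaffected. It is worth correcting because the baseline status is already collected and the change is small.

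**What to change.** 1. Reword the section 3.5 item to 180 days from randomisation, matching section 3.6, the analysis section and the Trial Summary.
2. Keep every randomised participant in the model. Define the modelled AMR outcome as the first isolate sampled after randomisation, and within 180 days of it, of an organism or resistance type (MRSA, VRE, ESBL or CPE) not recorded for that participant before randomisation.
3. Report any detection alongside it, adjusted for the Appendix 3 baseline AMR status.

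The cost is wording plus a derivation from sample dates, laboratory reports and the baseline field. There are drawbacks. Fewer events will be modelled. Because surveillance is passive, participants not cultured before randomisation will count as baseline negative, so some older resistance will still be classed as new. The rule must also say whether a different organism with the same resistance type counts as new; if it works by type alone, a later ESBL infection with another species would be missed in anyone ESBL-positive at baseline.

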#### Acute Kidney Injury (AKI)

The proportion of patients that experience AKI (as defined in Section 3.6) during the 180 days following randomisation will be reported by randomised group. This outcome will be modelled using a mixed effect logistic regression model with fixed effects for allocation, the stratification factors and other prognostic baseline covariates, and random intercepts for study recruitment site. The estimated conditional odds ratio for allocation, 95% confidence interval and p-value will be reported. To aid interpretability, point estimates and appropriate two-sided 95% confidence for the relative risk (cases/non-cases) and absolute risk reduction (based on the fitted model) will be reported, with the fixed effect covariates in the model set to various representative values (i.e. marginal risk ratios and risk differences at representative values). Average marginal effects on both the risk ratio and risk difference scales will also be reported with appropriate two-sided 95% confidence intervals.

The EXTEND Trial protocol ISRCTN no. 72819021

#### Days of ventilation

Days of ventilation during the 180 days following randomisation will be calculated as the number of days of intubation between randomisation and the final successful extubation. Successful extubation is defined as extubation and survival for at least 72 hours. Raw summaries of the number of days of ventilation between randomisation and 180 days post-randomisation will be reported by randomised group, both overall and by survival status. Death during intubation, or death during the 72 hours immediately following extubation will be ranked as worse than any number of days of ventilation without death. The empirical cumulative distribution function for this outcome will be plotted stratified by randomised group. This outcome will be analysed using a proportional odds model with fixed effects for allocation, the stratification factors and other prognostic baseline covariates and random intercepts for recruitment site. This model will be used to derive marginal effects (on both the risk ratio and risk difference scales) conditional on pre-specified representative values of the fixed effect covariates (e.g. Pr(Y > 5 | Intervention, X)/Pr(Y > 5 | Control, X) for covariates X). Average marginal effects (on both the risk ratio and risk difference scales) will also be reported together with appropriate 95% confidence intervals for various relevant outcomes/cut-offs.

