#### Source control procedures

The number, incidence and type of source control procedures occurring over the 180 days following randomisation will be reported descriptively by randomised group. The total number of source control procedures of different types (radiological, surgical) and source control procedures of any type occurring in each randomised group will be compared using a proportional odds model, with fixed effects for allocation, the stratification factors and other prognostic baseline covariates, and random intercepts for study recruitment site. This model will be used to derive the difference in mean number of source control procedures in each group, conditional on pre-specified representative values of the fixed effect covariates, as well marginal effects (on both the risk ratio and risk difference scales)

The EXTEND Trial protocol ISRCTN no. 72819021

conditional on pre-specified representative values of the fixed effect covariates (e.g. Pr(Y > 0 |Intervention, X)/Pr(Y > 0 | Control, X) for covariates X). Average marginal effects (on both the risk ratio and risk difference scales) will also be reported together with appropriate 95% confidence intervals for various relevant outcomes/cut-offs.

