#### Days/Nights in hospital

The total number of nights spent in hospital during the 180 days following randomisation, proportion of total follow up time in hospital and mortality will be reported descriptively by randomised group and overall. For analysis, death within 180 days following randomisation will be coded as the "worst"/"highest" outcome (i.e. death will be ranked worse than any number of nights in hospital without death). This outcome and its empirical cumulative distribution function will be plotted by randomised group and overall. Total number of nights in hospital (with death coded as the worst/highest outcome) will be compared using a proportional odds model, with fixed effects for allocation, the stratification factors and other prognostic baseline covariates, and random intercepts for study recruitment site. This model will be used to derive marginal effects (on both the risk ratio and risk difference scales) conditional on pre-specified representative values of the fixed effect covariates (e.g. Pr(Y > 28 | Intervention, X)/Pr(Y > 28 | Control, X) for covariates X). Average marginal effects (on both the risk ratio and risk difference scales) will also be reported together with appropriate 95% confidence intervals for various relevant outcomes/cut-offs.

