#### Number of episodes of treatment failure

The total number of episodes of treatment failure during the 180 days following randomisation will be reported descriptively by randomised group and overall. For analysis, death within 180 days following randomisation will be coded as the "worst"/"highest" outcome (i.e. death will be ranked worse than any number of treatment failure episodes without death). This outcome and its empirical cumulative distribution function will be plotted by randomised group and overall. Total number of episodes of treatment failure (with death coded as the worst/highest outcome) will be compared using a proportional odds model, with fixed effects for allocation, the stratification factors and other prognostic baseline covariates, and random intercepts for study recruitment site. This model will be used to derive marginal effects (on both the risk ratio and risk difference scales) conditional on pre-specified values of interest for the fixed effects (on both the risk ratio and risk ratio and risk difference scales) will also be reported together with appropriate 95% confidence intervals for various relevant outcomes/cut-offs.

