#### Re-admissions

The proportion of participants who are re-admitted to hospital during the 180 days following randomisation, and number of re-admissions per participant will be reported descriptively by randomised group and overall. The number of re-admissions per participant and empirical cumulative distribution function will also be plotted by randomised group and overall. The binary re-admission outcome (re-admitted vs not re-admitted during 180 days post-randomisation) will be modelled using a mixed effect logistic regression with fixed effects for allocation, the stratification factors and other prognostic baseline covariates, and random intercepts for study recruitment site. The estimated conditional odds ratio for allocation, 95% confidence interval and p-value will be reported. To aid interpretability, point estimates and appropriate two-sided 95% confidence intervals for the relative risk (cases/non-cases) and absolute risk reduction (based on the fitted model) will be reported, with the fixed effect covariates in the model set to various representative values (i.e. marginal risk ratios and risk differences at representative values). Average marginal effects on both the risk ratio and risk difference scales will also be reported with two-sided appropriate 95% confidence intervals. The count re-admission outcome (number of re-admissions during 180 days post-randomisation) will be analysed

using a proportional odds model, with fixed effects for allocation, the stratification factors and other prognostic baseline covariates, and random intercepts for study recruitment site. This model will be used to derive the difference in mean number of readmissions in each group, conditional on prespecified representative values of the fixed effect covariates, as well marginal effects (on both the risk ratio and risk difference scales) conditional on pre-specified representative values of the fixed effect covariates (e.g. Pr(Y > 0 | Intervention, X)/Pr(Y > 0 | Control, X) for covariates X). Average marginal effects (on both the risk ratio and risk difference scales) will also be reported together with appropriate 95% confidence intervals for various relevant outcomes/cut-offs.

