#### Days of renal replacement therapy

The number of days patients receive renal replacement therapy during the 180 days post randomisation will be reported by group, both overall and by survival status. For the purposes of analysis, death while receiving renal replacement therapy, or during the 72 hours following termination of renal replacement therapy will be ranked as worse than any number of days of renal replacement therapy without death. The empirical cumulative distribution function for this outcome will be plotted stratified by randomised group. This outcome will be analysed using a proportional odds model with fixed effects for allocation, the stratification factors and other prognostic baseline covariates and random intercepts for recruitment site. This model will be used to derive marginal effects (on both the risk ratio and risk difference scales) conditional on pre-specified representative values of the fixed effects (on both the risk ratio and risk difference scales) will also be reported together with appropriate 95% confidence intervals for various relevant outcomes/cut-offs.

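### Days of ventilation and of renal replacement rank death as worst only on support or within 72 hours of its end, so a patient who dies never supported gets the best score

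*Protocol*

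**What the plan says.** All the rules below stand in protocol section 10.2.4.

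- **Days of ventilation.** Days are "calculated as the number of days of intubation between randomisation and the final successful extubation". The protocol then says what counts as success: "Successful extubation is defined as extubation and survival for at least 72 hours". On death: "Death during intubation, or death during the 72 hours immediately following extubation will be ranked as worse than any number of days of ventilation"; the comparison is with patients who do not die.
- **Days of renal replacement therapy.** The worst rank is restricted in the same way: "death while receiving renal replacement therapy, or during the 72 hours following termination of renal replacement therapy will be ranked as worse". Here too the comparison is with patients who do not die, whatever their days of therapy.
- **Days/Nights in hospital.** Any death within 180 days is coded highest: "death will be ranked worse than any number of nights in hospital without death".
- **Number of episodes of treatment failure.** Again any death within 180 days: "death will be ranked worse than any number of treatment failure episodes without death".
- **Days of anti-microbial therapy.** Death is coded worst only if it occurs while the patient is still on antibiotics.

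Each of these outcomes goes into a proportional odds model. Section 10.2.1 includes all randomised participants with data for the outcome, and neither support outcome is limited to patients who were supported. Raw days of ventilation and of renal replacement are summarised overall and by survival status.

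**The concern.** On both scales fewer days is better and zero is best. If the only deaths moved to the worst end are those on support or within 72 hours of it, every other death is scored by its day count alone. For a patient who died on the ward without support, that count is zero. The model then treats some of the worst outcomes in the trial as ideal ones.

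If mortality differs between the arms, the ordinal odds ratios for these two outcomes mix a support effect with a mortality effect that is only partly counted. Usually this pulls the estimate towards no difference. In an unfavourable pattern of deaths it can make the arm with more deaths look slightly better. The plotted cumulative distribution functions of the ranked outcome have the same defect.

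**Working it through.** **1. Applying the written rule to patient types (ventilation)**

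| Patient | Score as written | Score if any death within 180 days is worst |
|---|---|---|
| Survivor, never intubated | 0 (best) | 0 (best) |
| Dies on the ward, never intubated | 0 (best) | worst |
| Intubated 2 days, dies on day 4 after extubation | 2 | worst |
| Survivor, intubated 10 days | 10 | 10 |
| Dies while intubated | worst | worst |

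Rows 1 and 2 are tied. Row 3 satisfies the definition of successful extubation, so it keeps its 2 days and ranks ahead of row 4. The same holds for renal replacement with days of therapy.

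**2. How many deaths could be affected**

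The protocol gives no expected mortality for the trial and no share of deaths off support. The UK observational study in section 1 had 11.3% mortality. Applied to 1166 patients: 0.113 × 1166 ≈ 132 deaths. Assumed shares off support and outside the 72-hour window give:

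- 25%: about 33 deaths not ranked worst
- 50%: about 66
- 75%: about 99

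**3. Effect on the odds ratio (illustration)**

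The protocol states no figure for these outcomes to reproduce. I used three levels: 0 days, more than 0 days, worst. Let d be mortality, v the proportion of survivors ventilated and s the share of deaths off support, all taken as never ventilated.

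- Written rule: (1−d)(1−v) + ds; (1−d)v; d(1−s)
- All deaths worst: (1−d)(1−v); (1−d)v; d

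A proportional odds model, logit Pr(Y ≥ k) = α_k + β × arm, was fitted by maximum likelihood to these proportions with equal arms. The result is exp(β) for intervention v control; below 1 favours intervention.

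*Case A: d = 14% control v 9% intervention, v = 8%, s = 50%*

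| Rule | Control (0 / >0 / worst) | Intervention (0 / >0 / worst) | Odds ratio |
|---|---|---|---|
| Written | 86.12 / 6.88 / 7.00% | 88.22 / 7.28 / 4.50% | 0.81 |
| All deaths worst | 79.12 / 6.88 / 14.00% | 83.72 / 7.28 / 9.00% | 0.72 |

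With 583 per arm, 583 × 0.14 × 0.5 ≈ 41 and 583 × 0.09 × 0.5 ≈ 26 deaths take the best score. For s from 30% to 70% the written-rule odds ratio runs from 0.77 to 0.88. If half of the off-support deaths had been ventilated earlier, it is 0.77 at s = 50%.

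*Case B: d = 11.3% v 10.3%, v = 8%, s = 50%.* Written 0.96; all deaths worst 0.93. With equal mortality both are 1.00.

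*Case C: d = 11.3% control v 16.3% intervention, v = 15%, the whole 5-point excess off support.* With 25%, 50% or 75% of control deaths off support, the written rule gives 0.95 to 0.96. All deaths worst gives 1.28.

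**The case against.** **Different rules for different outcomes may be deliberate.** Three outcomes that count days on a treatment (antimicrobials, ventilation, renal replacement) use death on or near that treatment; nights in hospital and failure episodes use any death. A reader might infer that the plan contradicts itself. It does not: each outcome has its own rule and the rules can stand together. What remains is an unexplained inconsistency, and the restricted rule still has the consequence shown in step 1.

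**The rule may leave off-support deaths unplaced.** The ranking is against days without death, so one can argue that other deaths have no rank at all. The outcome would then be undefined for those patients, and the same repair is needed. Nor is this detail left to the SAP, because the protocol itself fixes which deaths rank worst.

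**Other counts also lack a death rule.** A reader might extend the point to source control ("The number, incidence and type of source control procedures occurring over the 180 days following randomisation") and re-admissions ("The count re-admission outcome (number of re-admissions during 180 days post-randomisation) will be analysed"). The documents do not support that. Those sections state no wrong rule, section 10.2.4 leaves their detail to the SAP, and both derive a difference in mean number, which a top category for death would leave undefined.

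**The harm is limited.** These are secondary outcomes, all-cause mortality has its own time-to-event analysis, and raw days are shown by survival status, so a mortality difference would not be hidden. That stands and keeps the point moderate. It does not correct the modelled odds ratios.

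**The remedy has a price.** In Case A, control arm, deaths make up 7.00/13.88 = 50% of the non-zero outcomes under the written rule and 14.00/20.88 = 67% under the alternative. The outcome moves closer to a repeat of mortality. That is a fair reason to keep the present coding as a sensitivity analysis.

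**Conclusion.** The point holds for days of ventilation and days of renal replacement therapy. The stated rule gives the best score to patients who die never supported, and lets some who die later rank ahead of survivors with longer support. This follows from the text and needs no assumption.

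The numerical effect does need assumptions, because the protocol gives neither a mortality difference nor an off-support share. It ranges from negligible (0.96 v 0.93 in Case B, none with equal mortality) to clear dilution (0.81 v 0.72 in Case A). A reader might infer that the rule will reverse a mortality effect. That needs essentially all the excess deaths to fall off support (Case C), and even then the written rule gives a near-null 0.95 to 0.96, against 1.28. Dilution is the ordinary expectation; reversal is a possibility. No renal-replacement figure was computed; the argument there rests on the identical form of the rule.

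The change should be made, but it does not touch the primary analysis.

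**What to change.** In section 10.2.4, for the analysis of days of ventilation and of days of renal replacement therapy, code any death within 180 days of randomisation as the worst category, as is already done for nights in hospital and failure episodes. Keep the raw day summaries by survival status. Report the present on-support coding as a sensitivity analysis. Consider the same change for days of anti-microbial therapy, or state why its narrower rule is wanted. Leave the source control and re-admission counts as they are on this point.

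The cost is about one sentence per outcome and one extra model fit each; deaths are already collected. The downside is that mortality will drive these two outcomes more, which the text should say.
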